	
• Grade 3 or higher non-hematologic toxicity that are considered at least possibly related to Ibrutinib with the exception of nausea, vomiting, diarrhea, or electrolyte abnormality, unless these persist for at least 3 days despite maximal supportive care• Any grade 3 or higher fungal or bacterial infection (excluding line infection, catheter-associated UTI, or C difficile infection), cardiac toxicity (with the exception of hypertension) or bleeding regardless of the attribution. We note, though, that many patients in the hospital that develop infection of any grade will be treated with IV antibiotics, and that per CTCAE criteria, those graded 3 or higher would be those where IV antibiotics are indicated, not only for those where IV are chosen due to convenience.• Grade 3 or higher hemorrhage regardless of attribution, or Grade 2 hemorrhage that is considered at least possibly related to ibrutinib and is considered to be significant by the treating physician in collaboration with the PI.• Non COVID-19 related neutropenic fever 
Enrollment to this dose level will stop if 2 of the first 3 evaluable patients or if at least 33% of subsequent evaluable patients (i.e, 2/6, 3/9, or 4/12) have DLT. If unacceptable toxicity is observed, Ibrutinib will decrease to 280 mg daily, and another 12 patient lead-in will be evaluated at this lower dose level following the same stopping rules. If toxicity is acceptable, the study will proceed to the randomized component. Patients who do not receive 14 days of Ibrutinib for reasons other than toxicity or DLT will be replaced for the purposes of the safety and tolerability assessment.
 
Randomized Double-Blind Phase 2 Study
 
The main study is a randomized, double-blind placebo-controlled trial. Following completion of the safety lead-in, patients in the phase 2 portion will be randomized in a 1:1 fashion to receive ibrutinib plus standard treatment (Arm A) versus placebo plus standard treatment (Arm B) for COVID-19.
 
Patients may receive any additional therapies that are not prohibited in the section on concomitant medications.
 
In this trial, cycles will be 7 days in length. Study drug will continue for 2 cycles (14 days).

--	--

Accrual Expectations, N	78

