	
 • Measurement of T-cell repertoire and IgM, IgA, IgG response to SARS-CoV-2 over time among patients treated with ibrutinib (Arm A) versus control (Arm B) treatment; • Measurement of epigenetic age, clonal hematopoiesis, and MBL on treatment outcome • Measurement of serial change cytokines including (but not limited to) IL6, IL1B, TNF-alpha, IL-10 serum levels over time among patients treated with ibrutinib (Arm A) versus control (Arm B) treatment
Statistics/ Sample Size Estimate	
Safety Lead-In: 12 patients will be enrolled as part of the safety lead-in cohort. Enrollment to a dose level will stop if 2 of the first 3 evaluable patients or if at least 33% of subsequent evaluable patients (i.e, 2/6, 3/9, or 4/12) have DLT.
 
Randomized Phase 2: Allowing for roughly 10% over-accrual, we plan to randomize 66 high-risk patients with cancer to the two arms of the study in a 1:1 ratio utilizing a permuted block schedule. Randomization will be stratified on age (<60 years vs \geq 60 years) and presence of comorbidities (yes vs no) (comorbidities defined in Appendix C). The primary endpoint is the proportion of randomized patients with respiratory failure or death during hospitalization for COVID-19 infection within 30 days of registration.
 
Based on the study in China, we assume that the event rate is 40% and that it can be reduced to 15% when Ibrutinib is given in addition to standard care for COVID-19. With 60 patients and using a standard group sequential design, there is 82.8% power to detect a reduction in the event rate under the alternative hypothesis and constraining the one-sided type I error to 20%. Power was calculated using a z-test for the difference in two proportions, pooled variance, and adjustment for small sample sizes with the Casagrande-Pike-Smith correction (EAST v6.5; Cytel, Inc). There will be an interim analysis when 50% of randomized patients have been followed for 30 days from registration. The study will be stopped early if at the interim analysis the observed event rate is higher in the ibrutinib arm (Arm A) than in the control arm (Arm B). At the final analysis, data will be analyzed using a one-sided Fisher's exact test and a promising signal declared if $p \leq 0.20$ and the event rate is lower in the experimental arm.

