	
Although the actual reduction in the event rate could be larger than 25%, it could also be as low as 20% and still be quite meaningful. Furthermore, there is uncertainty in the event rate of the control arm. For these reasons, we have incorporated increased flexibility at the time of the interim analysis to potentially increase the sample size if conditional power indicates promising results, and will thus implement an adaptive group sequential design (Chen, DeMets, Lan; 2004).
 
At the interim analysis, there are 4 possible outcomes: 1) the futility criteria are met and the trial stops early; 2) the conditional power is unfavorable (<50%), and enrollment continues to the full 60 patients without an increase in sample size; 3) the conditional power is in a promising zone (defined as conditional power $\geq 50\%$ and $< 82.8\%$), and sample size may be re-estimated with the original sample size updated to boost the power to a target of 82.8%, subject to a maximum sample size of 120; or 4) the conditional power is favorable ($\geq 82.8\%$), and enrollment continues to the full 60 patients without an increase in sample size. When using this procedure, no adjustment to the final test statistic or critical value from the original design is required to control the Type I error rate. In addition, if the conditional power is in the promising zone, we can choose not to increase the sample size beyond what was originally planned or by a flexible amount without penalty.
 
Operating characteristics using the adaptive group sequential design is presented for four different scenarios:
 
Scenario 1: Event rates in the ibrutinib and control groups are 15% and 40%
 
Scenario 2: Event rates in the ibrutinib and control groups are 25% and 50%
 
Scenario 3: Event rates in the ibrutinib and control groups are 20% and 40%
 
Scenario 4: Event rates in the ibrutinib and control groups are 30% and 50%
 
For each scenario, the power and expected sample size is also provided for the standard group sequential design. For example, under Scenario 4, the power of the adaptive group sequential design has increased by 11.7% at the cost of corresponding average sample size increases of 11 patients. It is important to note that under the standard group sequential design, the power would have been only 64.7%. For the adaptive group sequential design, the conditional power falls in the promising zone 21.0% of the time, and for these simulations, the re-estimated sample size on average is 101 resulting in a boost in power to 89.2%.

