Design and Sample Size: Based on a study in China, we assume that the event rate is 40% with standard care and that the event rate can be reduced to 15% when Ibrutinib is added to standard care for COVID-19. With 60 patients and using a standard group sequential design, there is 82.8% power to detect a reduction in the event rate under the alternative hypothesis and constraining the one-sided type I error to 20%. Power was calculated using a z-test for the difference in two proportions, pooled variance, and adjustment for small sample sizes with the Casagrande-Pike-Smith correction (EAST v6.5; Cytel, Inc). There will be an interim analysis when 50% of randomized patients have been followed for 30 days from registration. The study will be stopped early if at the interim analysis the observed event rate is higher in the ibrutinib arm (Arm A) than in the control arm (Arm B). We will plan to over-accrue by about 10% for a total accrual goal of 66 patients.

Although the actual reduction in the event rate could be larger than 25%, it could also be as low as 20% and still be quite meaningful. Furthermore, there is uncertainty in the event rate of the control arm. For these reasons, we have incorporated increased flexibility at the time of the interim analysis to potentially increase the sample size if conditional power indicates promising results, and will thus implement an adaptive group sequential design (Chen, DeMets, Lan; 2004).

At the interim analysis, there are 4 possible outcomes: 1) the futility criteria are met and the trial stops early; 2) the conditional power is unfavorable ($<50\%$), and enrollment continues to the planned sample size without an increase in sample size; 3) the conditional power is in a promising zone (defined as conditional power $\geq 50\%$ and $< 82.8\%$), and sample size may be re-estimated with the original sample size updated to boost the power to a target of 82.8%, subject to a maximum sample size of 120; or 4) the conditional power is favorable ($\geq 82.8\%$), and enrollment continues to the planned

sample size without an increase in sample size. When using this procedure, no adjustment to the final test statistic or critical value from the original design is required to control the Type I error rate. In addition, if the conditional power is in the promising zone, we can choose not to increase the sample size beyond what was originally planned or by a flexible amount without penalty.

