Primary Endpoint Analysis: All randomized patients will be included in the primary endpoint analysis and analyzed in the treatment arm to which they were randomized (ITT population). The data will be analyzed using a one-sided Fisher's exact test and a promising signal declared if $p \leq 0.20$ and the event rate is lower in the experimental arm. Since the primary endpoint is to be measured within the first 30 days of registration, we do not expect that primary endpoint information will be missing. However, if there is data missing, the patient will be considered a treatment failure.

Sensitivity analyses include comparison between treatment arm when adjusting for stratification factors and other important variables such as type of cancer or more refined categories of standard of care therapy via logistic regression. If there are events for respiratory failure based on clinical diagnosis without an objective measure and driven solely by resource limitation or if patient has DNI (Do Not Resuscitate) status, a sensitivity analysis will compare arms excluding patients with these events. Sensitivity analyses will be performed for the ITT population and for eligible patients who receive their assigned therapy without a major protocol violation.

Adverse Event Stopping Rules: If there is no concerning safety signal in the lead-in cohort, and the study is able to continue to the randomized component as planned, we have included a plan for comparing toxicity at the interim analyses (first 30 patients across both arms). Accrual will be temporarily suspended to this study and discussion of the data with co-investigators and the data safety monitoring board will occur if we observe adverse events that satisfy the following criteria:

- If the percentage of grade 3/4 all-cause adverse events is at least 15% higher in the ibrutinib arm than in the standard of care arm. This would also include grade 2 hemorrhage if considered significant by the treating physician in collaboration with PI.
- If the percentage of grade 4 all-cause adverse events is at least 15% higher in the ibrutinib arm than in the standard of care arm
- If the percentage of grade 5 treatment-related adverse events is at least 5% higher in the ibrutinib arm than in the standard of care arm

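### The synopsis gives the planned randomized size as both 66 and 60, and every stated power and operating characteristic is for 60 although 66 would be analysed

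*Combined protocol and SAP*

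**What the plan says.** **Size behind the power.** The synopsis (Statistics/Sample Size Estimate) and Section 13 (Design and Sample Size) both tie 82.8% power to 60 patients. In the operating-characteristics tables the futility rows show 30 patients, the unfavorable and favorable rows 60.

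**Size to randomize.** The same synopsis cell plans to randomize 66. Section 13 agrees: "We will plan to over-accrue by about 10% for a total accrual goal of 66 patients".

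**Size after the interim.** For both the unfavorable and the favorable zone, the synopsis says that "enrollment continues to the full 60 patients without an increase in sample size". The matching rule in Section 13 refers to the planned sample size and gives no number.

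**Size analysed.** Section 13 (Primary Endpoint Analysis): "All randomized patients will be included in the primary endpoint analysis". A patient with a missing primary outcome is counted as a treatment failure.

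**Interim.** Both sections place it when half of the randomized patients have 30 days of follow-up. Adverse Event Stopping Rules in Section 13 puts the toxicity comparison at the interim and describes it as the "first 30 patients across both arms".

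**Total.** The synopsis row "Accrual Expectations, N" gives 78, and the monitoring schedule in Section 9.9 also ends at 78. In the promising zone the randomized size may be raised, "subject to a maximum sample size of 120". A second 12-patient lead-in is possible.

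**The concern.** Over-accrual usually covers patients who will drop out of the analysis, so that the analysed number comes back to the powered number. Here nobody drops out: the analysis includes all randomized patients and a missing outcome becomes a failure. Randomizing 66 therefore means analysing 66, a size for which the plan gives no power and no operating characteristics.

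Two practical questions are left open. After an interim in the unfavorable or favorable zone, the study team cannot tell from the synopsis whether to close enrolment at 60 or at 66. They also cannot tell whether the interim is due at 30 or at 33 patients. Both should be settled before anyone sees comparative data.

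A lesser point is that 78 stands alone as the accrual figure, with no total for a trial whose randomized part may reach 120.

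**Working it through.** **Inputs (synopsis and Section 13).** Control and ibrutinib event rates: 40/15% (Scenario 1), 50/25% (2), 40/20% (3), 50/30% (4). One-sided type I error 20%, allocation 1:1, pooled-variance z-test with the Casagrande-Pike-Smith correction. Stop for futility at half information if the ibrutinib event rate is the higher one.

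**Formulas.** With n per arm, control rate p_c, ibrutinib rate p_t, d = p_c − p_t and p̄ their mean:

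- corrected size per arm: m = (n − 1/d)² / n
- v = p_c(1 − p_c) + p_t(1 − p_t)
- θ = d·√(m/v)
- c = 0.8416·√(2p̄(1 − p̄)/v)
- power = Φ₂(θ√0.5, θ − c; correlation √0.5), the probability of passing the futility look and then rejecting. The efficacy boundary used in the simulations is so conservative that it is ignored here.

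**Step 1: reproduce the plan at 60 (n = 30), Scenario 1.**

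- m = (30 − 4)²/30 = 22.53
- v = 0.24 + 0.1275 = 0.3675
- θ = 0.25·√(22.53/0.3675) = 1.958
- c = 0.8416·√(0.39875/0.3675) = 0.877
- power = Φ₂(1.384, 1.081) = 82.8%, as stated

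**Step 2: the same at 66 (n = 33), Scenario 1.**

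- m = (33 − 4)²/33 = 25.48
- θ = 2.082, c unchanged
- power = Φ₂(1.472, 1.205) = 85.6%

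**Step 3: all scenarios, standard group sequential design.**

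| Scenario | Stated at 60 | Reproduced at 60 | Same method at 66 | Difference from stated (points) |
|---|---|---|---|---|
| 1 | 82.8% | 82.77% | 85.6% | 2.8 |
| 2 | 78.7% | 78.67% | 81.7% | 3.0 |
| 3 | 68.0% | 67.99% | 71.3% | 3.3 |
| 4 | 64.7% | 64.66% | 67.9% | 3.2 |

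All four stated figures reproduce at 60, so 60 is the size behind them.

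**Step 4: the planned final test.** Exact enumeration of the one-sided Fisher test at 0.20, with a futility look at 15 + 15, gives 86.6/80.1/72.2/65.7% at 60 and 87.5/82.5/72.7/69.0% at 66. The gain is 0.9, 2.4, 0.5 and 3.3 points. Moving the look to 16 or 17 per arm adds a further 0.2 to 0.6 points at 66.

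**Step 5: zones.** Current-trend conditional power was computed by the z-approximation for every 15 + 15 outcome that passes futility (136 outcomes), once with a final size of 60 and once with 66. No outcome changes zone.

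**Step 6: timing and totals.**

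- Interim: 66/2 = 33; 60/2 = 30.
- Accrual: 60 × 1.1 = 66; 12 + 66 = 78.
- At the cap with one 12-patient lead-in: 12 + 120 = 132.
- With two full lead-ins: 24 + 120 = 144.
- If the 10% also applies to the cap: 120 × 1.1 = 132 randomized, and 12 + 132 = 144 in total.

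**The case against.** The best defence is that nothing is hidden and nothing is miscalculated. The plan states both numbers and how they relate: 60 is the powered size, 66 is that plus about 10%. The sums are right. Section 13 does not repeat the synopsis phrase, so the direct contradiction is one sentence used for two zones. An interim at half of those randomized follows whatever number is randomized. The 30 in the toxicity rule leads to a pause and discussion, and a difference of three patients changes no test. All of this stands, and it keeps the point small.

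The margin above 60 also has a possible use. Counting missing outcomes as failures pulls the arms together. Suppose, as an assumption not in the documents, that a share f is missing in both arms, so each rate becomes p + f(1 − p). By the plan's method, Scenario 1 power at 66 is then 82.8% for f = 3% and 77.2% for f = 9%. The plan does not give this as the reason for over-accruing, and it would still leave 66 as the analysed size.

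A reader might go further on the total in three ways that the documents do not support:

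- **That 78 is a ceiling which the design breaks.** The row is headed as an expectation, Section 9.9 cites 78 only as an example, and the cap of 120 is stated openly in both sections.
- **That raising 78 after the interim would unblind staff.** This presumes that 78 is an approved limit, and no such approval is in the documents. Any increase already implies the promising zone, because only that zone allows one, whatever total was printed at the start.
- **That 132 or 144 is a firm maximum.** Lead-in patients who miss 14 days of drug for reasons other than toxicity are replaced, with no limit given, and the plan does not say whether over-accrual applies to 120.

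**Conclusion.** The point holds as an inconsistency in a number that the trial relies on. Within one synopsis cell the planned randomized size is 66 and, in two of the four interim outcomes, 60. Section 13 does not settle it, because its continuation rule carries no number. Under the stated analysis rules the analysed size would be 66, while every power, zone probability and expected size is for 60, and the interim is 33 or 30.

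The size is small. At 66 the power without re-estimation is 2.8 to 3.3 points above the stated figures by the plan's own method, and 0.5 to 3.3 points above the 60-patient value by exact Fisher enumeration. No interim outcome changes zone in the z-approximation. A reader might infer that the trial is underpowered; it is not, since the stated figures are conservative for 66.

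These results assume the stated event rates, equal arms and, except where noted, no missing outcomes. The adaptive-design powers and zone probabilities were not re-simulated at 66. The accrual figure of 78 needs a clearer label, no more.

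**What to change.** 1. State one planned randomized size in the synopsis and in Section 13 (Design and Sample Size, and Adverse Event Stopping Rules), and use that number in the unfavorable and favorable outcomes.
2. Set the efficacy interim and the toxicity comparison at half of that size.
3. Give power for that size. If it is 66, the fixed-size figures are about 85.6/81.7/71.3/67.9%, and the simulation table should be re-run with 66 as the starting size. If it is 60, the stated figures stand, the over-accrual sentence goes, and base-case accrual becomes 12 + 60 = 72.
4. Label 78 as base-case accrual (12 + 66). State beside it that up to 120 may be randomized after re-estimation, and say whether the 10% applies to 120. Note that total enrolment at the cap is then at least 132, and more with a second lead-in or replaced lead-in patients.

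The cost is wording plus, if 66 is chosen, one recalculation and one simulation run. No patient is added beyond what the design already allows.

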2.1. Primary Objective

Safety run-in

- To determine the feasibility and tolerability of administering Ibrutinib in COVID-19 infected patients

Phase 2

- To determine whether ibrutinib administration plus standard care for COVID-19 (Arm A) in cancer patients can diminish respiratory

failure or death as compared to untreated control population receiving placebo plus standard care (antiviral such as remdesivir or others, chloroquine, hydroxychloroquine, cytokine blocking peptides or small molecules) (Arm B). Respiratory failure is defined as any of the followings:

- Endotracheal intubation and mechanical ventilation
- Extracorporeal membrane oxygenation
- High-flow nasal cannula oxygen delivery (i.e., reinforced nasal cannula delivering heated, humidified oxygen with fraction of delivered oxygen ≥ 0.5 and flow rates of ≥ 30 l/min)
- Noninvasive positive pressure ventilation
- Clinical diagnosis of respiratory failure without initiation of one of above measures only when clinical decision-making is driven solely by resource limitation or if patient has DNI (Do Not Resuscitate) status.

2.2 Secondary Objectives

- To determine time to clinical resolution of need for supplemental oxygen (i.e. maintenance of oxygen saturation of 93% or greater on room air with ambulation) or need for supplemental oxygen above baseline for those on home oxygen.
- To determine rate of ICU admission and length of ICU admission for patients treated with ibrutinib (Arm A) versus control population receiving standard therapy (Arm B)
- To determine rate of shock requiring vasopressor support for patients treated with ibrutinib (Arm A) versus control population receiving standard therapy (Arm B)
- To determine the rate of secondary infection (bacterial, fungal, viral) for patients treated with ibrutinib (Arm A) versus control population receiving standard therapy (Arm B)
- To determine the time to hospital discharge for patients treated with ibrutinib (Arm A) versus control population receiving standard therapy (Arm B)
- To determine grade 3 or higher toxicity observed in patients treated with ibrutinib (Arm A) versus control population receiving standard therapy (Arm B)
- To determine time to mechanical ventilation, the number of days of mechanical ventilation per patient and total observed in patients treated with ibrutinib (Arm A) versus control population receiving standard therapy (Arm B)
- To determine the overall survival at 3 and 12 months post-enrollment.

Exploratory Objectives

- To determine the time to defervescence (oral temperature<100.5 degrees F for a 48 hour time period) among patients treated with ibrutinib (Arm A) versus control population receiving standardtherapy (Arm B)
- To examine the impact of baseline clinical features (e.g. type of cancer, active therapy), duration of symptoms prior to admission and laboratory features (e.g. T cell count) on outcome for patients treated on this therapeutic study
- To determine the proportion of patients with viral clearance at end of ibrutinib therapy, time of hospital discharge and follow up thereafter among patients treated with ibrutinib (Arm A) versus control (Arm B) treatment
- To determine the time and proportion of patients who develop IgM and IgG levels toward SARS-CoV-2 treated with ibrutinib (Arm A) versus control treatment (Arm B)
- To examine immune cell subsets for absolute number, activation, exhaustion markers, and presence of maturation arrest (NK cells) at baseline and over time among patients treated with ibrutinib (Arm A) versus control (Arm B) treatment
- To examine T-cell repertoire over time among patients treated with ibrutinib (Arm A) versus control (Arm B) treatment
- To determine the influence of epigenetic age, clonal hematopoiesis, and monoclonal B cell lymphocytosis (MBL) on treatment outcome
- To determine serial change in inflammatory markers as CRP, ferritin, D-Dimer and cytokines including IL6, IL1B, and TNF-alpha serum levels over time among patients treated with ibrutinib (Arm A) versus control (Arm B) treatment

3. Study Endpoints

